**Investigator Interests:**

Does the principal investigator, or do any research personnel who are responsible for the design, conduct or reporting of this project or any of their family members (spouse or dependent child) have an incentive or interest, financial or otherwise, that may affect the protection of the human subjects involved in this project, the scientific objectivity of the research or its integrity? Note: The Principal Investigator (Project Director), upon consideration of the individual's role and degree of independence in carrying out the work, will determine who is responsible for the design, conduct, or reporting of the research.

See Disclosures and Management of Personal Interests in Human Research

<http://www.yale.edu/hrpp/policies/index.html#COI>

Yes       No

Do you or does anyone on the research team who is determined by you to be responsible for the design, conduct or reporting of this research have any patent (sole right to make, use or sell an

invention) or copyright (exclusive rights to an original work) interests related to this research protocol?

Yes             No

If yes to either question above, list names of the investigator or responsible person:

*The Yale University Principal Investigator, all Yale University co-investigators, and all Yale University individuals who are responsible for the design, conduct or reporting of research must have a current financial disclosure form on file with the University's Conflict of Interest Office. Yale New Haven Hospital personnel who are listed as con-investigators on a protocol with a Yale University Principal Investigator must also have a current financial disclosure form on file with the University's Conflict of Interest Office. If this has not been done, the individual(s) should follow this link to the COI Office Website to complete the form:*

<http://www.yale.edu/coi/>

NOTE: The requirement for maintaining a current disclosure form on file with the University's Conflict of Interest Office extends primarily to Yale University and Yale-New Haven Hospital personnel. **Whether or not they are required to maintain a disclosure form with the University's Conflict of Interest Office, all investigators and individuals deemed otherwise responsible by the PI who are listed on the protocol are required to disclose to the PI any interests that are specific to this protocol.**

**Billing Information:** IRB Review fees are charged for projects funded by Industry or Other For-Profit Sponsors. If this study is funded by Industry or Other For-Profit Sponsor, provide the Name and Address of the Sponsor Representative to whom the invoice should be sent. *Note: the PI's home department will be billed if this information is not provided.*

**SECTION I: GENERAL INFORMATION**

1. **Performing Organizations:** Identify the hospital, in-patient or outpatient facility, school or other agency that will serve as the location of the research. Choose all that apply:

**b. External Location[s]:**

- |  |  |
|--|--|
|  APT Foundation, Inc.                                  |  Haskins Laboratories                  |
|  Connecticut Mental Health Center           |  John B. Pierce Laboratory, Inc.       |
|  Clinical Neuroscience Research Unit (CNRU) |  Veterans Affairs Hospital, West Haven |

Other Locations, Specify: International Research Site  
(Specify location(s)):

2. **Probable Duration of Project:** State the expected duration of the project, including all follow-up and data analysis activities.

9 years

3. **Research Type/Phase: (Check all that apply)**

a. **Study Type** Single Center Study Multi-Center StudyDoes the Yale PI serve as the PI of the multi-site study? Yes  No  Coordinating Center/Data Management Other:b. **Study Phase** N/A Pilot Phase I Phase II Phase III Phase IV

4. Is this study a clinical trial? Yes  No

*NOTE the current ICMJE (International Committee of Medical Journal Editors) definition of a clinical trial: "any research study that prospectively assigns human participants or groups of humans to one or more health-related interventions to evaluate the effects on health outcomes." Health-related interventions include any intervention used to modify a biomedical or health-related outcome (for example, drugs, surgical procedures, devices, behavioral treatments, dietary interventions, and process-of-care changes). Health outcomes include any biomedical or health-related measures obtained in patients or participants, including pharmacokinetic measures and adverse events"*

If yes, where is it registered?

Clinical Trials.gov registry 

Other (Specify)

Registration of clinical trials **at their initiation** is required by the FDA, NIH and by the ICMJE.

*If this study is registered on clinicaltrials.gov, there is new language in the consent form and compound authorization that should be used.*

For more information on registering clinical trials, including whether your trial must be registered, see the YCCI webpage, <http://ycci.yale.edu/researchers/ors/registerstudy.aspx> or contact YCCI at [contact])

5. Will this study have a billable service as defined by the [Billable Service Definition](#)?

Yes  No 

If you answered "yes", this study will need to be set up in Patient Protocol Manager (PPM)

<http://medicine.yale.edu/ymg/systems/ppm/index.aspx>

6. Are there any procedures involved in this protocol that will be performed at YNHH or one of its affiliated entities? Yes \_\_\_ No X *If Yes, please answer questions a through c and note*

instructions below. *If No, proceed to Section II.*

- a. Does your YNHH privilege delineation currently include the **specific procedure** that you will perform?
- b. Will you be using any new equipment or equipment that you have not used in the past for this procedure?
- c. Will a novel approach using existing equipment be applied?

If you answered “no” to question 6a, or "yes" to question 6b or c, please contact the YNHH Department of Physician Services ([name]) for prior approval before commencing with your research protocol.

## SECTION II: RESEARCH PLAN

1. **Statement of Purpose:** State the scientific aim(s) of the study, or the hypotheses to be tested.

The acetylcholinergic (ACh) system is critically involved in learning, memory, arousal and attention, functions that are substantially impaired in many neuropsychiatric conditions. For example, Alzheimer’s disease (AD) is associated with decreased cholinergic function, whereas recent evidence suggests increased and decreased cholinergic function in major depression and schizophrenia, respectively. Cholinergic function is also fundamentally impaired in nicotine addiction. *In vivo* molecular imaging studies of muscarinic and nicotinic receptors have provided substantial contributions to our understanding of these disorders, but these contributions were limited by the lack of a method suitable to measure fluctuations in synaptic ACh level.

We recently developed and tested an innovative molecular imaging method in humans to detect changes in brain synaptic ACh levels, using single photon emission computed tomography (SPECT), the beta2-nicotinic acetylcholine receptor ( $\beta_2$ -nAChR) radioligand [ $^{123}$ I]5-IA-85380 (5-IA) and the acetylcholinesterase (AChE) inhibitor, physostigmine, challenge. Results suggest elevated ACh levels induced by physostigmine lead to a reduction in the availability of nicotinic receptors for the binding of the radioligand. If validated, this paradigm might provide a very useful method to interrogate presynaptic cholinergic function in health and disease. To date, receptor imaging of the ACh system at Yale has been limited to 5-IA and SPECT. SPECT is known to have poorer resolution and less reliable quantification compared to positron emission tomography (PET). Furthermore, the slow kinetic of this radiotracer requires lengthy imaging sessions, which is not well tolerated in impaired populations. [ $^{18}$ F]NCFHEB (NCFHEB) has been recently introduced as a superior  $\beta_2$ -nicotinic PET imaging agent (1, 2). This proposal outlines a series of studies aiming at testing the suitability of PET and NCFHEB to examine genetic polymorphisms that modulate nAChR availability and to detect changes in ACh synaptic levels, as well as to determine the effect of nicotine on nAChR availability.

This innovative paradigm will lay the groundwork for future studies that can directly interrogate ACh function in the living human brain. This is critical to the advancement of our understanding of ACh involvement in psychiatric and medical disorders.

Additionally, a substantial literature body demonstrates that nAChRs and the cholinergic system dynamically control the mesolimbic DA system by enhancing, inhibiting, and filtering striatal DA release. We have preliminary data suggesting tobacco smokers at 2 weeks of abstinence have blunted DA release compared to nonsmokers. We propose in Aim 7 to determine 1)

whether there is reduced DA release in smokers at 2 weeks of withdrawal vs. nonsmokers, 2) if the magnitude of DA release is correlated with alterations in ACh levels measured in Aim 4 and 3) if alterations in DA and ACh predict relapse vulnerability.

**Aim 1: To determine the test-retest reproducibility of NCFHEB binding parameters in 10 nonsmoking subjects.**  $\beta_2$ -nAChRs will be quantified twice in nonsmoking subjects. Based on preclinical evidence, we hypothesize within 20% difference of binding parameters between test and retest scans.

**CLOSED Aim 2: To determine if  $\beta_2$ -nAChR availability is genetically predisposed in never smokers and smokers** We propose to determine if the ANKK1 genotype (rs4938015/hCV38879) or CHRNA4 genotype determines  $\beta_2$ -nAChR availability in adult never smokers. Specifically, 10 never smokers and 10 smokers at one week of abstinence will be imaged using NCFHEB PET and blood samples for DNA extraction will be collected from all subjects.

**Hypothesis:** Homozygotes (TT) will have higher  $\beta_2$ -nAChR availability compared to age-, and sex matched heterozygotes that carry the C allele in the ANKK1 gene (rs4938015/ hCV38879).

**CLOSED Aim 3: To determine if the adaptive increase in  $\beta_2$ -nAChR availability and change in  $\beta_2$ -nAChR availability over the first month of abstinence in smokers is genetically predisposed.** We will determine if ANKK1 or CHRNA4 genotypes are associated with changes in  $\beta_2$ -nAChR availability in smokers over time recruited in aim 2. The same smokers from Aim 2 will be supported to maintain abstinence for 4-8 weeks. Smokers that successfully abstain for 4-8 weeks (~ 50%; e.g. 5 smokers) will be imaged a second time using NCFHEB and PET. The % change in  $\beta_2$ -nAChR availability will be determined as the difference in NCFHEB binding  $[(V_T/f_p @7\text{days of abstinence} - V_T/f_p @4\text{ wks abstinence})/V_T/f_p @7\text{ days abstinence}]$ . Blood samples for DNA extraction will be collected from all subjects.

**Hypothesis:** Based on our preliminary data we hypothesize that smokers that carry the A allele for hCV16178933/rs2273504 or the G allele for hCV15953820/rs2236196 genotype will have higher  $\beta_2$ -nAChR availability at 7-9 days of abstinence compared to never smokers matched for age and sex and genotype. Whereas smoker homozygotes (GG and AA respectively for hCV16178933/rs2273504 or for hCV15953820/rs2236196) will demonstrate similar  $\beta_2$ -nAChR availability compared to never smokers. We also hypothesize that CC homozygotes for the CHRNA4 rs2273502 will show a pronounced decrease in  $\beta_2$ -nAChR availability while carriers of the T allele show no change in  $\beta_2$ -nAChR availability will demonstrate the greatest change or normalization over 6 weeks of abstinence.

**Aim 4: To measure the sensitivity of NCFHEB binding to changes in endogenous ACh levels in smoking and nonsmoking subjects.** After baseline quantification of  $\beta_2$ -nAChR availability, physostigmine will be administered as previously described (HIC#09100005837) and subjects will be scanned again with NCFHEB. We hypothesize there will be greater increase in ACh level (or greater reduction in radio tracer binding) in smoking as compared to nonsmoking subjects. These results will be correlated with changes in mood and cognition associated with physostigmine administration. Up to 50 smoking and 50 nonsmoking subjects will participate. Smokers that are able to remain abstinent will have a second set of baseline and post-physostigmine scans with NCFHEB 4-8 weeks later. This will allow us to determine whether ACh function changes over the course of abstinence.

**CLOSED Aim 5: To measure the sensitivity of NCFHEB binding to changes in endogenous ACh levels in smoking and nonsmoking subjects with schizophrenia.** After baseline quantification of  $\beta_2$ -nAChR availability, at 1 week of smoking abstinence, physostigmine will be administered as previously described (HIC#09100005837) and subjects will be scanned again with NCFHEB. We hypothesize there will be greater increase in ACh level (or greater reduction in radio tracer binding) in smoking as compared to nonsmoking subjects with schizophrenia, but the extent of this change will be different than in controls. These results will be correlated with changes in mood, negative and positive symptoms, and cognition associated with physostigmine administration. Up to 10 smoking and 10 nonsmoking subjects with schizophrenia will participate.

**Aim 6: To determine the efficacy of a bolus to infusion scan versus a bolus scan of NCFHEB with physostigmine challenge.** We will invite back never smokers and smokers who completed bolus scans in Aim 4 to complete one bolus to infusion scan with NCFHEB with physostigmine administration. Smokers will complete the scan at approximately one week of abstinence from smoking. We will compare the results from this scan to their Aim 4 bolus scans to determine which administration better suits a physostigmine challenge. Smokers who completed all 4 scans in Aim 4 will not be asked to return within the same year.

**CLOSED Aim 7. To determine amphetamine-induced DA release in tobacco smokers during acute withdrawal and in nonsmokers.** Smoker and nonsmoker subjects from Aim 4 will participate. Each subject will participate in up to 2 [ $^{11}\text{C}$ ]PHNO PET scans (ideally, the two PET scans will be carried out in the same day). Up to three hours before the second PET scan, amphetamine (0.5 mg/kg, PO) will be administered. In smokers, the scan will occur at 10-30 days of smoking abstinence. We hypothesize that at 10-30 days of withdrawal amphetamine-induced DA release will be blunted compared to healthy nonsmokers.

**CLOSED Aim 8. To determine the degree of occupancy of the  $\beta_2^*$ -nAChRs by nicotine after use of an e-cig compared to a tobacco cigarette using [ $^{18}\text{F}$ ]NCFHEB PET neuroimaging.** Given recent evidence that experienced e-cig users can achieve similar plasma nicotine levels compared to tobacco smoking, we hypothesize there will not be a significant difference in  $\beta_2^*$ -nAChR occupancy by nicotine after use of an e-cig as compared to a regular cigarette. We will also examine arterial plasma nicotine levels and compare to nicotine occupancy of the nAChRs between groups.

2. **Background:** Describe the background information that led to the plan for this project. Provide references to support the expectation of obtaining useful scientific data.

The cholinergic system, and the beta2-nicotinic acetylcholine receptors ( $\beta_2$ -nAChRs) specifically, have been implicated in many neuropsychiatric conditions, such as addiction, depression, schizophrenia and AD.(3-6) This involvement has been supported by molecular imaging studies of the  $\beta_2$ -nAChR, including studies performed by our group at Yale.(7-13) The  $\beta_2$ -nAChRs are the most abundant nAChRs in the brain. Until very recently,  $\beta_2$ -nAChR SPECT and PET radiotracers available for human use displayed slow kinetics, requiring prolonged scanning sessions(14, 15), and practically eliminated our ability to study severely impaired patients.(16, 17) The recently introduced radiolabeled antagonist (-)-2-(6-(18)F-fluoro-2,3'-bipyridin-5'-yl)-7-methyl-7-azabicyclo[2.2.1]heptane ([ $^{18}\text{F}$ ]NCFHEB or NCFHEB) has been

shown to have high binding potential at the  $\beta_2$ -nAChRs and rapid kinetics (1) and is thus a very promising new radioligand. The reproducibility of NCFHEB  $V_T$  measurement in humans and the sensitivity of NCFHEB  $V_T$  to changes in extracellular ACh concentrations have not yet been reported. Here, we propose to test the reproducibility of NCFHEB *in vivo* binding in humans and to examine its vulnerability to changes in synaptic ACh. These critical studies will answer a fundamental question regarding use of NCFHEB and PET in the study of cholinergic systems and will have broad implications to the future studies of severe neuropsychiatric conditions (nicotine addiction, mood disorder, schizophrenia, AD), with high relevance to individual and public health. If validated, such an imaging tool would have enormous potential to facilitate the development of innovative medicines aimed at modulating the cholinergic system.

Furthermore, since nicotine binds with high affinity to the  $\beta_2$ -nAChRs and there is a high prevalence of smoking in the US, we will examine this system and its response to increases in endogenous ACh in healthy smokers and the associated cognitive and genetic factors.

**Evidence for Genetic Inheritance of Tobacco Smoking** A family history of tobacco smoking is a powerful predictor of smoking risk. Children of ever- or current- smokers are more likely to smoke, compared to children of never smokers (18-22). Smokers with a family smoking history are more likely to be persistent smokers than those with no history (23-26). Regular stable smoking in adolescence is related to having a current parent smoker relative to a former or never smoker parent (27). Failure to quit smoking is linked to having parents that smoked daily (19, 28, 29). Parental smoking is related to a greater likelihood of developing nicotine dependence, higher numbers of cigarettes smoked per day, higher anxiety levels and a trend towards depression (24, 30). While all smokers experience anxiety in response to stressor, only family history positive smokers experience heightened craving for cigarettes (31). *These data suggest that there is a biological difference between family history positive smokers and family history negative smokers that is likely transmitted between generations through shared genetics.*

There is strong evidence to support genetic transmission of smoking between family members. Ever-smoking segregates in families following expectations consistent with a dominant Mendelian genetic factor with a frequency of 0.02. Studies of monozygotic and dizygotic twins reared together and apart suggest that there is 50-72% inheritance rate (26, 32-44). The concordance rate amongst monozygotic twins is higher than dizygotic twins, regardless of whether they were raised together or separately [reviewed by (45)]. Genetics contributes to the initiation of smoking behavior (25, 26, 34, 43) with heritability estimates of 0.11 and 0.78 whereas shared and unique environmental effects range between 0.00 and 0.59 and 0.07 and 0.36 respectively [reviewed by (46, 47)]. Persistence of smoking is also determined by genetics with heritability estimates between 0.04 and 0.86 [reviewed by (46, 47)]. An analysis of 17,500 monozygotic and dizygotic twin pairs from 14 studies, estimated that genetics accounted for 56%, whereas shared and unique environmental factors accounted for 24 and 20% of the liability for smoking initiation, and genetics accounted for 67%, whereas shared and unique environmental factors accounted for 2 and 31% of the liability for smoking persistence.

Smoking behavior has been linked to chromosomes 1, 2, 4, 5, 6, 9, 10, 11, 14, 17, 18 and 21 (48-51). A recent genome-wide association study of nicotine dependent individuals showed that single nucleotide polymorphisms (SNPs) nominate candidate genes coding for cell adhesion, enzymes, transcriptional regulators, neurotransmitters, and receptors and the regulation of DNA, RNA, and proteins are associated with successful abstinence from smoking (52). In marker based genetic studies, associations between smoking behavior and several candidate genes have been

evaluated including cytochrome p450, dopamine receptor (D2) dopamine transporter, serotonin transporter and the nicotinic acetylcholine receptor [reviewed by (46)]. Variants in genes occur due to insertions, deletions, variable numbers of repeats, and single nucleotide polymorphisms (SNPs) in the DNA sequence. SNPs are the most common type of polymorphism occurring as frequently as once for every 200-1000 base pairs in different regions of the genome. SNPs have been targeted because they may be used either as synonymous markers for linkage, and linkage disequilibrium mapping, or they may represent functional mutations themselves. This limitation may be dealt with by doing a haplotype analysis of multiple SNPs. Haplotypes provide greater statistical power compared to SNPs (53).

**Nicotinic Acetylcholine Receptor (nAChR)** Nicotine initiates its effects in brain through the nicotinic acetylcholine receptor (nAChR). Neuronal nAChR belong to a receptor family of ligand gated ion channel receptors that include the GABAA and GABAC, glycine and 5-HT3 receptors. Neuronal nAChR are comprised of 5 subunits (54). Each subunit spans the membrane 4 times such that the second transmembrane domain forms the wall of the ionic pore that transports Ca2+. To date, 12 genes coding for subunits associated with the neuronal nAChR have been identified from the mammalian genome including  $\alpha_1$ ,  $\alpha_2$ ,  $\alpha_3$ ,  $\alpha_4$ ,  $\alpha_5$ ,  $\alpha_6$ ,  $\alpha_7$ ,  $\alpha_9$ ,  $\beta_1$ ,  $\beta_2$ ,  $\beta_3$ ,  $\beta_4$ , [reviewed by (55)]. Neuronal nAChR comprised of  $\alpha_7$  and  $\alpha_9$  are functional as monomeric receptors which are pharmacologically characterized by low affinity for nicotinic agonists, and high affinity for  $\alpha$ -bungarotoxin, while all other  $\alpha$  subunits (e.g.  $\alpha_1$ ,  $\alpha_2$ ,  $\alpha_3$ ,  $\alpha_4$ ,  $\alpha_5$ ,  $\alpha_6$ ,  $\alpha_8$ ,  $\alpha_{10}$ ) require co-expression of  $\alpha$  and  $\beta$  pairs and are distinguished by their high affinity for nicotinic agonists and low affinity for  $\alpha$ -bungarotoxin (56, 57). Binding sites for the endogenous neurotransmitter, acetylcholine, are highly conserved between subunit types whereas nicotine has higher affinity for the  $\alpha_4$  and  $\alpha_3$  subunits versus the  $\alpha_2$ ,  $\alpha_3$ ,  $\alpha_4$ , or  $\alpha_6$  and  $\beta_2$  or  $\beta_4$  subunits (58). Acetylcholine binds to heteromeric nAChRs at the interface between  $\alpha_2$ ,  $\alpha_3$ ,  $\alpha_4$ , or  $\alpha_6$  and  $\beta_2$  or  $\beta_4$  subunit (59). The fifth accessory subunit, which is not involved in acetylcholine binding may be  $\beta_2$ , or  $\beta_4$ , or  $\alpha_5$  or  $\beta_3$  (59). The  $\beta_3$  and  $\alpha_5$  subunits are likely partners with  $\alpha_6$  subunits in nAChR forming a pentamer of  $\alpha_6\alpha_4\alpha_3\alpha_5$  that are localized to dopaminergic cell bodies (60). nAChR  $\alpha_4\beta_2$  receptors demonstrate 4-fold lower amplitude whole cell currents, and slower acute desensitization and functional rundown as compared to  $\alpha_7$ -containing nAChR. Beta subunits influence the sensitivity of  $\alpha_4$  to functional inactivation. The second major intracellular loop influences the acute desensitization of nAChR (61). Nicotinic agonists have higher functional potency at  $\alpha_4$  containing versus  $\beta_2$  containing but they have higher binding affinity at  $\beta_2$  containing nAChR(62). High and low affinity  $\alpha_4\beta_2$ nAChR result from the assembly of  $\alpha_4$  and  $\beta_2$  into two distinct stoichiometric arrangements ( $\alpha_4$ )2( $\beta_2$ )3 high affinity; and ( $\alpha_4$ )3( $\beta_2$ )2, low affinity that differ significantly in their functional and pharmacological properties [reviewed by(63)]. The ( $\alpha_4$ )2( $\beta_2$ )3 stoichiometry is more sensitive to activation and upregulation by nicotine and desensitizes more slowly. Importantly, agonist binding to nAChR likely reflects multiple states, including the resting and desensitized states (62).

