### 3.7 Statistical analysis.

**3.7 a Power Analysis in Never Smokers:** Assuming Hardy-Weinberg equilibrium, the allele frequency predicts that 30 will be homozygous (CC); 25 will be heterozygous (CT) and 5 will be homozygous (TT) for the ANKK1 alleles, and 11 will be homozygous (AA) 29 will be heterozygous (AG) and 20 will be homozygous (GG) for the CHRNA5 alleles. In a one-way ANOVA analysis, sample sizes of 30, 25, and 5 are obtained from the three genotypes of ANKK1 whose means are to be compared. The total sample of 30 subjects achieves 0.96 power to detect differences among the means versus the alternative of equal means using an F test with a 0.05 significance level for thalamus. The size of the variation in the means is represented by their standard deviation which is 17.49. The common standard deviation within a group is assumed to be 32.30. The other powers are 0.95, 0.87, and 0.99 for ANKK1 for the brain regions of striatum, cerebellum and cortex, respectively. We have enough power to detect the effect with the proposed sample size. We aim to recruit at least 10 subjects that are homozygous for TT; if we do not achieve our goals for the rarer genotype by the end of year 3; we will screen subjects prior to imaging them in year 4.

**3.7.b Power Analysis in Smokers:** The group means of  $\alpha_2$ -nAChR availability for the heterozygotes of hCV16178933/rs2273504 or hCV15953820/rs2236196 are higher in smokers than non-smokers in the brain regions of striatum, cerebellum and mean cortex, but not thalamus. We can achieve 0.81 power to detect a difference of 11.7 in striatum between the null hypothesis that both group means are 97.5 and the alternative hypothesis that the mean of non-smoking group is 85.8 with estimated group standard deviations of 14.9 and 10.8 and with a significance level (alpha) of 0.05000 using a one-sided two-sample t-test for hCV16178933/rs2273504. The other powers are 0.97, 0.95 for hCV16178933/rs2273504 and for cerebellum and mean cortex, respectively. The differences do not present in the homozygote subjects. We can also achieve 0.98 to 0.99 for hCV15953820/rs2236196 in the brain regions of striatum, cerebellum and mean cortex.

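### The Aim 3 hypothesis covers all carriers of A at rs2273504 or G at rs2236196, but the 0.81 power offered for it is for heterozygotes only, at group sizes the plan does not have

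*Combined protocol and SAP*

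**What the plan says.** All references are to the NCFHEB protocol in the combined file.

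**Hypothesis.** Section II, item 1 (Statement of Purpose), Aim 3, states that "smokers that carry the A allele for hCV16178933/rs2273504 or the G allele for hCV15953820/rs2236196 genotype will have higher" availability at 7-9 days of abstinence than never smokers matched on age, sex and genotype. It then limits the group expected to show no difference: "Whereas smoker homozygotes (GG and AA respectively for hCV16178933/rs2273504 or for hCV15953820/rs2236196) will demonstrate similar" availability. The null group is therefore GG at rs2273504 and AA at rs2236196.

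**Power.** Section 3.7.b (Power Analysis in Smokers), repeated under Smokers in item 12 (Statistical Considerations), says that mean availability values "for the heterozygotes of hCV16178933/rs2273504 or hCV15953820/rs2236196 are higher in smokers than non-smokers" in striatum, cerebellum and mean cortex. It continues "We can achieve 0.81 power to detect a difference of 11.7 in striatum", "with estimated group standard deviations of 14.9 and 10.8" and "with a significance level (alpha) of 0.05000 using a one-sided two-sample t-test for hCV16178933/rs2273504". It also says, without naming a genotype, "The differences do not present in the homozygote subjects". No group size is given.

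**Sample.** The Aim 2 paragraph of item 1 plans "10 never smokers and 10 smokers at one week of abstinence". Aim 3 uses the same smokers. Both aims are marked closed.

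**The concern.** Carrying an allele means having one copy or two. As written, the Aim 3 hypothesis puts AG and AA at rs2273504, and AG and GG at rs2236196, on the side expected to be higher. The power paragraph supports only the AG part of each group, and its remark about homozygotes can be read as saying that AA and GG show nothing.

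Two things are at stake. First, a reader will take 0.81 as the power for the stated hypothesis, when it belongs to a narrower group. Second, nothing says where AA at rs2273504 or GG at rs2236196 go in the comparison. With 10 smokers, moving one or two subjects between groups could change the result, and a grouping chosen after genotypes and scans are seen is not a planned one.

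**Working it through.** **1. The genotypes side by side**

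| SNP | Genotype | Aim 3 hypothesis | Power text, read literally |
|---|---|---|---|
| rs2273504 | AG | higher | higher |
| rs2273504 | AA | higher (carries A) | no difference |
| rs2273504 | GG | similar | no difference |
| rs2236196 | AG | higher | higher |
| rs2236196 | GG | higher (carries G) | no difference |
| rs2236196 | AA | similar | no difference |

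The two sources differ only in the AA row for rs2273504 and the GG row for rs2236196.

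**2. What 0.81 requires.** Inputs from section 3.7.b: difference 97.5 − 85.8 = 11.7; SDs 14.9 and 10.8; one-sided alpha 0.05. Power comes from the noncentral t distribution with Welch degrees of freedom, and with n per group the noncentrality is 11.7 / √[(14.9² + 10.8²)/n] = 11.7 / √(338.65/n).

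- n = 16: 11.7 / 4.60 = 2.54, power 0.798
- n = 17: 11.7 / 4.46 = 2.62, power 0.820
- n = 10: 11.7 / 5.82 = 2.01, power 0.611

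The stated 0.81 cannot be reproduced outright because its group size is missing. Solved backwards, it corresponds to about 16 to 17 heterozygotes per group with equal groups (a normal approximation gives 0.816 at 16). The planned 10 and 10 would give 0.61 only if every subject were heterozygous.

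**3. What happens if the tested group is carriers.** The documents give no allele frequency for either SNP, so the carried-allele frequency q is assumed to lie between 0.1 and 0.5. Under Hardy-Weinberg equilibrium the share of carriers who are homozygous is s = q² / [q² + 2q(1 − q)] = q / (2 − q).

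Suppose, as the literal reading has it, that these homozygotes show no smoker difference. Suppose also that the never-smoker mean is the same in both carrier genotypes. Then the carrier difference is 11.7(1 − s), and the smoker variance is 14.9² + 11.7² s(1 − s), taking 14.9 as the smoker SD.

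| q | s | Difference | Smoker SD | Power, 10 carriers per group | Power, 16 | Power, 17 |
|---|---|---|---|---|---|---|
| heterozygotes only | 0 | 11.7 | 14.9 | 0.61 | 0.80 | 0.82 |
| 0.1 | 0.053 | 11.1 | 15.1 | 0.56 | 0.75 | 0.78 |
| 0.3 | 0.176 | 9.6 | 15.6 | 0.46 | 0.63 | 0.66 |
| 0.5 | 0.333 | 7.8 | 15.9 | 0.34 | 0.48 | 0.50 |

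**4. How many subjects are involved.** Ten carriers per group is itself generous, because the 10 smokers are of all genotypes. The expected number of carriers among 10 is 10[1 − (1 − q)²], which is 1.9, 5.1 and 7.5 at q = 0.1, 0.3 and 0.5. Of these, 10q² = 0.1, 0.9 and 2.5 would be homozygous for the carried allele.

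The remaining power figures in the paragraph (0.97 and 0.95 for cerebellum and cortex; 0.98 to 0.99 for rs2236196) come without differences or SDs and cannot be checked.

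**The case against.** The strongest reply is that this is loose terminology. Aim 3 itself uses the word homozygotes for exactly GG at rs2273504 and AA at rs2236196, so the unqualified remark in the power text may mean only those two groups. The Aim 2 hypothesis speaks of heterozygotes carrying the C allele, so carrying may have been meant as heterozygous. The evidence cited for rs2236196 in the CHRNA4 background compares AG with AA and does not address GG. On this reading AA at rs2273504 and GG at rs2236196 are left out, not contradicted.

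That stands as far as it goes. A reader might infer that the plan's own data show no effect in these homozygotes, or that they are counted on opposite sides of an analysis. The documents do not establish either. The homozygote remark does not say which homozygotes it covers, and the only Aim 3 test described is the t-test inside the power calculation; no analysis population is given. Nor do the documents call A or G here the risk or the minor allele, or give a frequency for it, so neither label should be used.

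It is also fair that the dilution is small at q = 0.1, that the larger losses need a commoner allele together with zero effect in the homozygotes, and that the aim is closed with few subjects. Matching never smokers on genotype does not settle the matter, since it does not say which genotypes are pooled.

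What the reply does not remove is the mismatch. On the narrow reading the carrier hypothesis still includes genotypes for which no effect is estimated, and 0.81 still belongs to heterozygotes.

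**Conclusion.** The point holds as a mismatch between the written hypothesis and the group behind its power. The hypothesis covers carriers; the 11.7 and the 0.81 cover heterozygotes. Homozygotes for the carried allele are either inconsistently described or unassigned, depending on how the homozygote remark is read, and a flat contradiction is not proven.

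Two sizes should be kept apart. The shortfall from 0.81 to 0.61 at 10 per group follows from the documents' own inputs and arises whichever genotype group is used; it is the firmer result. The further fall to between 0.56 and 0.34 at 10 carriers per group depends on an assumed allele frequency of 0.1 to 0.5, Hardy-Weinberg proportions and no effect in those homozygotes. The figures at 16 and 17 per group show what 0.81 would require; they do not describe the planned study.

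**What to change.** State one grouping of the three genotypes at each SNP and use it in the Aim 3 hypothesis, section 3.7.b and item 12. Keep the carrier hypothesis as stated, and report AA at rs2273504 and GG at rs2236196 separately. Then do one of the following:

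- restate the striatal difference and power for carriers at the planned sample size, giving the group sizes and the allele frequency assumed; or
- label 0.81 as applying to heterozygotes only at about 16 to 17 per group, and call the carrier comparison exploratory.

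Do not reword the hypothesis to heterozygotes. The aim is closed, and that would narrow it after the fact to the group in which an effect had already been seen. If the comparison has already been run, record the grouping that was used.

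The cost is a few sentences and a lower power figure. No extra subjects, scans or assays are needed.
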